5.5.1 Allowed therapy

Patients should receive adequate supportive care if appropriate, including but not limited to:

- Antiemetic and anti-diarrheal medication
- Blood derived-products
- Bone resorption inhibitors after appropriate oral examination and counseling for oral hygiene.
- Local corticosteroids, including inhaled, intranasal, topical or intra-articular compounds.
- Systemic corticosteroids at a dose \leq 20 mg prednisone equivalent.
- Anticoagulation with LMWH, or subcutaneous or oral Factor Xa inhibitor for prophylactic or therapeutic uses.
- Non-live vaccines are allowed including toxoid and recombinant vaccines.
- Hormonal therapy

5.5.2 Prohibited therapy

Any other therapy administered for the treatment of kidney cancer, either approved or experimental, is prohibited. This includes but is not limited to chemotherapy, immunotherapy, herbal therapy, or other alternative systemic therapy targeting kidney cancer. Any investigational medical device is prohibited.

Therapeutic oral vitamin K inhibitors are prohibited. The platelet anti-aggregatory compound clopidogrel is also prohibited.

Live vaccines are prohibited during the course of study.

Immunosuppressive agents are prohibited during the course of study participation. Systemic steroids, at doses greater than the equivalent of 20 mg prednisone daily, may not be used.

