5.4 Definition of Dose-limiting Toxicity

For patients treated in arm 2, DLT will be defined as any abemaciclib or MK-6482 related toxicity resulting in discontinuation or dose reduction per the guidelines in the Section 6.2 to 6.87 within the first 28 days of treatment, for which there is no clear alternative explanation (i.e. disease related).

DLTs will be defined as any of the following events not clearly due to the underlying disease or extraneous causes:

- Any death
- Non-hematologic toxicity:
 - Grade 3 or higher
 - Hy's law cases
- Hematologic toxicity (for non-acute leukemia indications):
 - Grade 4 neutropenia for more than 7 days
 - Grade 3 or higher thrombocytopenia with clinically significant bleeding
 - Neutropenic fever

The DLT definition may exclude:

- Grade 3 nausea/vomiting or diarrhea for less than 72 hours with adequate antiemetic and other supportive care
- Grade 3 or higher electrolyte abnormality that lasts up to 72 hours, is not clinically complicated, and resolves spontaneously or responds to conventional medical interventions
- Grade 3 or higher amylase or lipase that is not associated with symptoms or clinical manifestations of pancreatitis

Patients within arm 2 who do not receive at least 80% of the intended abemaciclib plus MK-6482 doses during the first 28 days for reasons other than toxicity, will not be evaluable for DLTs and will be replaced. Once a tolerable dose combination has been determined in arm 2, patients will no longer be replaced in the study.

Dose escalation will proceed within each cohort according to **Table 4**. Dose-limiting toxicity (DLT) is defined above.

Table 4. Dose-escalation scheme

Number of Participants with DLT at a Given Dose Level	Escalation Decision Rule
0 out of 3	Enter 3 participants at the next dose level.
≥ 2	Dose escalation will be stopped. This dose level will be declared the maximally administered dose (highest dose administered). Three (3) additional participants will be entered at the next lowest dose level if only 3 participants were treated previously at that dose.

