6. DOSING DELAYS/DOSE MODIFICATIONS

Stringent inclusion and exclusion criteria as well as close monitoring of both serious and non-serious adverse events aim at ensuring the safety of the participants in this study. All AEs will be defined and graded according to the National Cancer Institute – Common Terminology Criteria for Adverse Events (NCI CTCAE) v5.0. Safety monitoring includes physical examination, laboratory assessments, as well as serial interval histories. All serious adverse events and protocol-defined events of interest will be specifically reported. Investigators and the overall PI will review adverse events on a regular basis during the study.

Dose delays and modifications will be made as indicated in the following tables. The descriptions and grading scales found in the revised NCI-CTCAE version 5.0 will be utilized for dose delays and dose modifications. A copy of the CTCAE version 5.0 can be downloaded from the CTEP website http://ctep.cancer.gov/protocolDevelopment/electronic_applications/ctc.htm.

Regarding treatment-related side effects, abemaciclib and MK-6482 have different adverse event profiles related to their therapeutic class. Some of these adverse events overlap. Management of adverse events potentially attributed to all study compounds, guidelines for dose delays or dose modifications should apply to all study drugs. If an adverse event is attributed to a specific compound, management of dose delays or modifications should be done independently.

Examples of events of particular interest, by frequency or severity, related to abemaciclib include neutropenia, diarrhea, elevated liver function tests. Examples of events of particular interest, by frequency or severity, related to MK-6482 include anemia, edema, fatigue, diarrhea, nausea.

In general, adverse events should be managed with appropriate supportive care. Dose modifications or delays have to be considered in case of unacceptable toxicity and ineffective symptomatic treatment, in order to prevent aggravation of toxicities. Decision of dose delays or reduction may occur at any time, at the discretion of the investigator. Interruption of all study compounds during a period longer than 12 weeks should lead to study discontinuation, unless specific approval by the overall PI.

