6.8 Interstitial lung disease (ILD)/Pneumonitis

General Guidance for Interstitial lung disease (ILD)/Pneumonitis events

Interstitial lung disease (ILD) / pneumonitis has been identified as an adverse drug reaction for abemaciclib. Adverse events reported included events such as interstitial lung disease, pneumonitis, obliterative bronchiolitis, organizing pneumonia, pulmonary fibrosis. The majority of events were Grade 1 or Grade 2 with serious cases and fatal events reported.

Monitor for clinical symptoms or radiological changes indicative of ILD/pneumonitis and please ask patients to report any new or worsening pulmonary symptoms. Symptoms may include hypoxia, cough, dyspnea, or interstitial infiltrates on radiologic exams.; these symptoms should be investigated and treated as per local clinical practice and/or guidelines (including corticosteroids as appropriate). Infectious, neoplastic, and other causes for such symptoms should be excluded by means of appropriate investigations. Investigations may include imaging such as high resolution computer tomography (HRCT), bronchoalveolar lavage (BAL), and biopsy as clinically indicated (see also Table 13: *refer to dose adjustment table for interstitial lung disease/pneumonitis*).

Table 13: Dose Modification and Management — Interstitial Lung Disease/Pneumonitis

Toxicity	Arm 1 – abemaciclib alone	Arm 2 – Abemaciclib plus MK-6482
Grade 1 or 2	No dose modification is required.	No dose modification is required.
Persistent or recurrent Grade 2 toxicity that does not resolve with maximal supportive measures within 7 days to baseline or Grade 1	Suspend dose until toxicity resolves to baseline or Grade 1. Resume at next lower dose.	Hold abemaciclib and MK-6482 until resolution of toxicity to baseline or grade 1. Resume abemaciclib at lower dose level. Resume MK-6482 at lower dose level.
Grade 3 or 4	Discontinue abemaciclib.	Discontinue abemaciclib and MK-6482.

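### Section 5.5.2 caps systemic steroids at 20 mg prednisone equivalent with no adverse-event exception, while 6.8 directs guideline steroid treatment of pneumonitis with no dose limit, and nothing says which rule governs

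*Combined protocol and SAP*

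**What the plan says.** Three places in the combined protocol and SAP bear on this.

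- **Section 5.5.1 (allowed therapy)** lists "Systemic corticosteroids at a dose" of no more than 20 mg prednisone equivalent among permitted supportive care.
- **Section 5.5.2 (prohibited therapy)** turns that limit into a ban: "Systemic steroids, at doses greater than the equivalent of 20 mg prednisone daily, may not be used". A separate sentence deals with other agents: "Immunosuppressive agents are prohibited during the course of study participation". Neither sentence has an exception for managing toxicity.
- **Section 6.8 (ILD/pneumonitis)** describes a recognised reaction to abemaciclib. Of the reported cases it says: "The majority of events were Grade 1 or Grade 2 with serious cases and fatal events reported". On new or worsening lung symptoms it says "these symptoms should be investigated and treated as per local clinical practice and/or guidelines (including corticosteroids as appropriate", and it gives no dose ceiling and no reference to 5.5.

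Table 13 in 6.8 covers study-drug dosing only. For grade 1 or 2 the entry is "No dose modification is required". Grade 2 that persists or recurs despite full supportive treatment is held and later resumed at a lower dose. Grade 3 or 4 leads to discontinuation. Section 6 adds a general discretion: "Decision of dose delays or reduction may occur at any time, at the discretion of the investigator".

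**The concern.** A site treating pneumonitis has two instructions. One sets a ceiling on systemic steroids in unqualified terms; the other sends the site to its own guideline and names steroids as part of the treatment. If the guideline dose is above 20 mg daily, the site cannot follow both.

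A site that reads 5.5.2 literally may limit indicated treatment of a known drug reaction. A site that follows its guideline gives a prohibited medication, and may then have to report a violation for what 6.8 told it to do. In a multi-center trial, different sites may resolve this differently.

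**Working it through.** The plan states no figure to reproduce and no arithmetic applies. The check is whether the two rules can be followed together, and for which patients they cannot.

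**Step 1: by steroid dose.** At or below 20 mg prednisone equivalent daily, 5.5.1, 5.5.2 and 6.8 can all be followed. Above 20 mg, 5.5.2 forbids what 6.8 may require. The conflict therefore exists only above the cap.

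**Step 2: by grade, using Table 13.**

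| ILD/pneumonitis | Study drug under Table 13 | Does the 5.5.2 cap still bind? |
|---|---|---|
| Grade 1 | No change required | Yes; a conflict arises only if the guideline dose exceeds 20 mg |
| Grade 2 | No change required | Yes; conflict if more than 20 mg is needed |
| Grade 2, persistent or recurrent | Hold, then resume at a lower dose | Yes; the patient remains on protocol therapy and a hold does not lift the cap |
| Grade 3 or 4 | Discontinue | Not on a sensible reading (step 3) |

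The persistent grade 2 row is the clearest case. Table 13 presupposes that supportive treatment has been taken as far as it can go, while 5.5.2 limits one form of that treatment.

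**Step 3: after treatment stops.** Section 5.5.2 also bars any other kidney cancer therapy, with no end date. Yet 5.7 follows patients for their next line of systemic treatment, and 5.6 has alternative care discussed when protocol therapy ends. The prohibitions in 5.5.2 therefore cannot have been meant to continue after discontinuation, and grade 3 or 4 events fall largely outside the conflict.

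**Step 4: is there a precedence rule?** Sections 5.5 to 5.7, section 6, 6.2, 6.8 and the other mentions of corticosteroids (3.2.7 and footnote 15 of the study calendar) contain none. Section 5.6 does not list use of a prohibited medication as a reason to stop protocol therapy. By contrast, 5.5.3 tells sites to avoid strong CYP3A inhibitors and then says what to do when one cannot be avoided. Section 5.5.2 has no such provision.

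**Step 5: how departures are classed.** Appendix C, 3.9.2, allows a change without prior IRB approval when it is needed to remove an apparent immediate hazard. Under 3.9.1, any other departure not approved in advance is a violation. Grade 2 pneumonitis treated above 20 mg could fall on either side.

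**Step 6: size.** The expected number affected would be (patients on abemaciclib) × (probability of grade 2 ILD while on or held from drug) × (probability of needing more than 20 mg, given that). The documents supply neither probability, so no number follows.

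**The case against.** The strongest reply is that an ordinary reading already reconciles the text. Section 6.8 is the specific rule for a named reaction and expressly mentions corticosteroids, so it should override a general restriction. The list in 5.5.1 is open-ended. Section 6 directs adverse events to suitable supportive care. The investigator may hold drug at any time, or under 5.6 may take the patient off therapy for an unacceptable adverse event. Grade 3 or 4 events lead to discontinuation and immediate hazards are excused, so little remains.

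Much of this stands, and it sets the limits of the point. It does not remove the conflict. That 6.8 overrides is plausible, but no text says so, and 5.5.2 is worded as a flat prohibition. An open-ended list in 5.5.1 cannot permit what 5.5.2 forbids by dose. Holding drug leaves the cap in place. Ending protocol therapy only to escape a concomitant-medication rule would be a poor outcome for a patient whom Table 13 would keep on, or return to, treatment.

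A reader might infer more than the documents support:

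- **That the bans run through follow-up**, because the immunosuppressant sentence refers to study participation and 5.7 continues survival follow-up for up to 2 years. Step 3 shows why 5.5.2 cannot sensibly be read that way.
- **That all of the up to 37 planned patients are affected**, since both arms receive abemaciclib. Only those who develop ILD/pneumonitis and need more than 20 mg meet the conflict.
- **That immunosuppressants in general should be exempted.** Section 6.8 names corticosteroids only, and 3.2.11 shows concern about life-threatening infection on myelosuppressive therapy. A blanket exemption would go too far.

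**Conclusion.** The conflict holds in a narrow form. Section 5.5.2 prohibits systemic steroids above 20 mg prednisone equivalent daily without an adverse-event exception, 6.8 directs steroid treatment of ILD/pneumonitis without a limit, and the available text does not rank them. It bites mainly for grade 2 events in patients on, or temporarily held from, study drug who need more than the cap.

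The size is unknown. Whether grade 2 treatment exceeds 20 mg at a given site is an assumption; the point requires only that 6.8 permits it and 5.5.2 does not. The consequence is for individual safety and violation reporting. Objective response, MTD determination, power and sample size do not depend on it. The case for acting is that a stated rule, followed literally, could cap treatment of a known drug reaction, and that correction costs almost nothing.

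**What to change.** Add to the steroid sentence of 5.5.2: *except systemic corticosteroids used to treat ILD/pneumonitis per section 6.8, with notification of the overall PI; such use is not a protocol violation.* Cross-reference the exception in 5.5.1 and 6.8.

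Leave holds and dose reductions to Table 13 and to investigator discretion under section 6. In particular, do not tie a mandatory dose reduction to steroid use. Section 5.4 counts as a DLT "any abemaciclib or MK-6482 related toxicity resulting in discontinuation or dose reduction per the guidelines" in the first 28 days, so such a clause could create DLTs in arm 2. A temporary hold alone is neither a discontinuation nor a reduction, so that argument does not apply to holds. Leave the ban on other immunosuppressive agents as it is.

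The cost is one clause, two cross-references and a PI notification when the exception is used, with no added visits, procedures or patients. The downside is that a few patients may receive higher-dose steroids while on or held from study drug. Section 5.5 already requires that use to be recorded as concomitant medication.

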5.5.3 Restricted therapy

Local anticancer therapies can be considered in case of progression or clinical indication. Those include radiation therapy, thermal ablation, surgery. Limited data are available with abemaciclib and radiotherapy. Thus, caution should be exercised with coadministering abemaciclib with radiotherapy. Sponsor must be contacted in these situations to ensure adequate risks related to the procedure and concomitant study treatment. In this situation where a target lesion is treated by such procedure, the participant may continue the study but may not be evaluable for response. However, the patient might remain evaluable for progression after discussion with the study sponsor.

Abemaciclib is predominantly cleared by oxidative metabolism via CYP3A4. Clinical drug interaction studies with a CYP3A inhibitor and CYP3A inducer significantly altered the PK of abemaciclib and its circulating major metabolites.

CYP3A inducers:

Avoid concomitant use of CYP3A inducers (**Appendix B**) and consider alternative agents.

CYP3A inhibitors:

Avoid concomitant use of strong CYP3A inhibitors (for example, voriconazole) and use caution with coadministered moderate (for example, ciprofloxacin) or weak (for example, ranitidine) CYP3A inhibitors. If coadministration with a strong CYP3A inhibitor is unavoidable, reduce the abemaciclib dose by one dose level (**Table 5**) or, in the case of ketoconazole, reduce the abemaciclib dose by two dose levels. In patients who have had a dose reduction by one dose level due to adverse reactions, further reduce the abemaciclib dose to dose level -2 (**Table 5**). Avoid grapefruit or grapefruit juice. If a CYP3A inhibitor is discontinued, increase the abemaciclib dose (after 3-5 half-lives of the inhibitor) to the dose that was used before starting the inhibitor.

In vitro studies in primary cultures of human hepatocytes indicate that abemaciclib might inhibit the metabolism of CYP2B6 substrate drugs in vivo. Based on this finding, sensitive substrates of CYP2B6 such as bupropion and efavirenz should be substituted or avoided if possible.

5.6 Criteria for Taking a Participant Off Protocol Therapy

Duration of therapy will depend on individual response, evidence of disease progression and tolerance. In the absence of treatment delays due to adverse event(s), treatment may continue until one of the following criteria applies:

- Disease progression
- Intercurrent illness that prevents further administration of treatment
- Unacceptable adverse event(s)
- Participant demonstrates an inability or unwillingness to comply with the oral medication regimen and/or documentation requirements

- Participant decides to withdraw from the protocol therapy
- Pregnancy
- General or specific changes in the participant's condition render the participant unacceptable for further treatment in the judgment of the treating investigator

Participants will be removed from the protocol therapy when any of these criteria apply. The reason for removal from protocol therapy, and the date the participant was removed, must be documented in the case report form (CRF). Alternative care options will be discussed with the participant.

When a participant is removed from protocol therapy and/or is off of the study, the participant's status must be updated in OnCore in accordance with REGIST-OP-1.

The overall PI must be notified in case of unusual or life-threatening adverse events.

5.7 Duration of Follow Up

After removal from protocol therapy, participants will be followed for safety for 90 days, or until initiation of new cancer-directed treatment, or until death, whichever occurs first.

Participants removed from protocol therapy with ongoing treatment-related adverse event(s) will be followed until resolution or stabilization of the adverse event(s), initiation of new cancer-directed treatment, or death.

Participants removed from protocol who did not experience disease progression will be followed as per protocol until progression, initiation of new cancer-directed treatment, or death.

Participants will be followed for survival and next line of systemic treatments every 6 months, until death or 2 years after treatment discontinuation. Follow-up will be performed by phone calls and review of health records.

5.8 Criteria for Taking a Participant Off Study

Participants will be removed from study when any of the following criteria apply:

- Lost to follow-up
- Withdrawal of consent for data submission
- Death

The reason for taking a participant off study, and the date the participant was removed, must be documented in the case report form (CRF). In addition, the study team will ensure Off Treatment/Off Study information is updated in OnCore in accordance with DF/HCC policy REGIST-OP-1.

5.9 Replacement

Participants that would be taking off study before receiving any dose of the study drugs will not be part of the analysis, such participant will be replaced. Participants who are enrolled on study but do not reach time of first imaging assessment (8 weeks) will not be evaluable and may be replaced.

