14.2 Sample Size and Accrual

There is limited data regarding clinical activity of abemaciclib and MK-6482 in ccRCC. Activity of abemaciclib has been described in a phase 1 trial in solid tumors that did not involve ccRCC patients¹⁴. Response rates in advanced refractory breast cancer patients treated with abemaciclib single agent was 19.5%¹⁵.

MK-6482 is has been evaluated in a phase I/II trial involving patients with refractory ccRCC. Preliminary data showed that among 55 patients treated at the MTD, objective response rate was 22%. Toxicities involved mainly anemia, hypoxia and edema. Drug discontinuations due to adverse events were less than 10%.

Therefore, in arm 1, planned sample size is 11 patients, allowing a 0.80 probability to observe 2 or more responses if the true ORR is 25% or higher.

Arm 2 will evaluate two dose levels and follow a standard 3+3 dose escalation scheme. Once the MTD is determined and 6 patients have been treated at the MTD, 14 additional patients will be enrolled for a total of 20 patients treated at the MTD. As ORR is 20-25% for ccRCC patients treated with MK-6482 single-agent, we target an ORR of 50% for the combination of abemaciclib plus MK-6482. With a planned sample size of 20 patients treated at the MTD, there is 94% power to distinguish an ORR of 50% from an ORR of 20% under one-stage design (one-sided alpha=0.09). The combination is considered effective if 7 or more responses are observed out of 20.

The total enrollment will be up to 37 patients (11 in arm 1 and 23~26 patients in arm 2). The accrual is expected to be 3-4 patients per month for a duration of 12 months to complete enrollment.

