14.3 Statistical Analysis

14.3.1 Analysis Datasets

The following Analysis datasets are planned for this study:

Full Analysis Set (FAS): The FAS will include all eligible patients who receive at least one dose of protocol therapy. All efficacy endpoints will be analyzed using the FAS Population.

Safety Analysis Set: Safety analysis will be conducted using the Safety Analysis Set defined as any participant receiving one dose of study treatment.

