14.3.2 Efficacy Analysis (arm 1 and 2)

Number and percent of patients who achieve overall response (CR or PR) by RECIST 1.1 will be summarized with 80% two-sided exact binomial confidence intervals (CI) in the FAS cohort. Subjects who have non-evaluable response, withdraw or die prior to the first response evaluation will be conservatively counted as non-responders in the primary analysis of ORR.

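### Section 5.9 permits replacement of dosed patients who miss the 8-week scan, in conflict with 5.4, and the arm 2 rule of 7 in 20 has no cut-off if more than 20 are dosed at the MTD

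*Combined protocol and SAP*

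**What the plan says.** **Replacement.** Section 5.9 first deals with patients who never receive a dose: they leave the analysis and are replaced. A second sentence then covers enrolled patients who "do not reach time of first imaging assessment (8 weeks) will not be evaluable and may be replaced". Undosed patients have already been dealt with, so this sentence reaches dosed ones, and it names no arm or phase. Section 5.4 replaces arm 2 patients who are not DLT-evaluable, then adds: "Once a tolerable dose combination has been determined in arm 2, patients will no longer be replaced in the study".

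**Analysis.** Section 14.3.1: "The FAS will include all eligible patients who receive at least one dose of protocol therapy". Under 14.3.2, patients whose response cannot be evaluated, or who "withdraw or die prior to the first response evaluation will be conservatively counted as non-responders in the primary analysis of ORR". ORR is "summarized with 80% two-sided exact binomial confidence intervals (CI) in the FAS cohort".

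**Decision rule and size.** In 14.2, after six patients at the MTD, "14 additional patients will be enrolled for a total of 20 patients treated at the MTD". The stated design is 20% against 50% ORR, 94% power, one-sided alpha 0.09. "The combination is considered effective if 7 or more responses are observed out of 20". On numbers: "The total enrollment will be up to 37 patients (11 in arm 1 and 23~26 patients in arm 2").

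**The concern.** The sections give different answers for a patient dosed at the MTD who leaves before week 8. Section 5.9 calls the patient not evaluable and allows a substitute. Section 5.4 allows none once the tolerable combination is settled. Section 14.3 keeps the patient as a non-responder. Section 12.1.1 adds a further mismatch, because it treats objective progression before the end of cycle 1 as evaluable.

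If such a patient is replaced, 14.3 retains both the patient and the substitute, and the number dosed at the MTD can pass 20. Section 14.2 does not say whether the rule then applies to the first 20 dosed, the 20 who reached week 8, or everyone dosed, and it gives no cut-off for a larger number. Keeping 7 gives the arm extra chances to reach the threshold, because certain non-responders are exchanged for patients who may respond. What is at stake is the false-positive rate of a co-primary efficacy decision.

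**Working it through.** **1. The plan's own figures.** Inputs from 14.2: n = 20, success at 7 or more, ORR 20% (null) and 50% (target).

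- Alpha = P(Bin(20, 0.20) ≥ 7) = 0.0867, which rounds to the stated 0.09.
- Power = P(Bin(20, 0.50) ≥ 7) = 0.9423, matching the stated 94%.
- Neighbouring cut-offs do not fit: 6 gives alpha 0.196 and 8 gives 0.032.

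**2. Model for replacement.** A replaced patient left before the first scan and is a certain non-responder. Let d be the share of dosed patients lost before week 8. The documents give no value, so d is assumed at 1%, 5%, 10%, 15% and 20%. Under the null the ORR is 20% in all dosed patients, as 14.3 defines it, so among those who stay it is pe = 0.20/(1 − d). The cut-off stays at 7.

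**3. Room for replacements.** The arm 2 range is 23 = 3 + 20 to 26 = 6 + 20. With three patients at the other dose level, 26 − 3 = 23 can be dosed at the MTD. With six there, 26 − 6 = 20 and no replacement fits. The cap of 23 is inferred from these figures; the plan does not state it.

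**4. Three readings.**

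- *A: 5.9 applies throughout.* Dosing continues until 20 are retained or 23 are dosed. Alpha = Σ(L = 0 to 3) C(19+L, L) d^L (1−d)^20 × P(Bin(20, pe) ≥ 7) + Σ(r < 20) P(Bin(23, 1−d) = r) × P(Bin(r, pe) ≥ 7).
- *B: 5.4 confines replacement to the first six at the MTD, and all their early losses are replaced.* Alpha = P(Bin(6, pe) + Bin(14, 0.20) ≥ 7). This is an upper bound for this reading.
- *C: as B, but only half of those losses fall before 5.4 bars replacement (assumption).* The formula is that of B with pe = 0.20/(1 − d/2).

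| Assumed early loss d | 1% | 5% | 10% | 15% | 20% |
|---|---|---|---|---|---|
| A: 5.9 throughout, cap 23 | 0.091 | 0.108 | 0.128 | 0.143 | 0.152 |
| B: first six only, at most | 0.088 | 0.093 | 0.100 | 0.108 | 0.118 |
| C: half of B's losses | 0.087 | 0.090 | 0.093 | 0.096 | 0.100 |

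Without the cap, reading A is P(Bin(20, pe) ≥ 7), which passes 0.09 at d of about 0.85%. The chance of at least one early loss among the first six is 1 − (1 − d)^6. For d of 5%, 10%, 15% and 20% this is 0.26, 0.47, 0.62 and 0.74.

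**5. Fixed-N reference.** P(Bin(N, 0.20) ≥ 7) is 0.109, 0.133 and 0.160 at N = 21, 22 and 23. These apply to a sample size set in advance.

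**6. The planned interval.** The 80% exact interval is 20.7% to 51.8% for 7/20 and 19.6% to 49.7% for 7/21.

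**The case against.** The strongest reply is that the plan already contains the answer. Section 5.4 is the specific rule for arm 2, while 5.9 is general and only permissive. Sections 1.1 and 14.2 define the 20 as patients treated at the MTD, not patients evaluable. Section 14.3.2 anticipates early leavers. The 23 to 26 range is explained without any replacements, and 15.5 has the investigator guard against over-accrual. One could follow 5.9 for enrolment and 14.3 for analysis without contradiction.

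Much of this stands. If 5.4 governs, the inflation is modest, and at low loss there is none beyond the stated 0.09. It does not close the gap. No text says that 5.4 prevails over 5.9. Section 5.4 itself replaces dosed patients for DLT evaluability before the tolerable combination is settled, and those patients stay in the FAS. With seven dosed and then the fixed 14, the count is 7 + 14 = 21, for which no cut-off exists.

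Four stronger readings are tempting and are not supported:

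- *Any replacement takes alpha above 0.09.* This fails under 5.4 at low loss: 0.088 at 1% in reading B, and 0.0897 at 5% in reading C.
- *The fixed-N values 0.109, 0.133 and 0.160 are the error rates after one, two or three replacements.* They are not. A replaced patient is a certain non-responder, not one more draw at 20%, so a loss rate is needed.
- *The ORR estimate is biased.* The FAS keeps early leavers in the denominator. Section 5.9 removes only undosed patients from the analysis.
- *The 80% interval is a second success criterion.* Section 14.3.2 uses it as a summary. A declared success at 7/21 would merely sit beside an interval that includes 20%.

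**Conclusion.** The concern holds in a limited form. Sections 5.9 and 5.4 conflict in the current text, 5.9 sits badly with 14.3, and 14.2 has no cut-off for more than 20 dosed at the MTD. Confidence in these points is high.

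Confidence in the size is moderate. If dosed patients are replaced and 7 is kept, the false-positive rate rises from 0.087 to roughly 0.108–0.152 at 5–20% early loss when 5.9 applies throughout, and to at most 0.093–0.118 when 5.4 confines replacement to the first six. This rests on assumed loss rates, on no responses among early leavers, on a null ORR of 20% in all dosed patients and, for the first range, on the inferred cap of 23. With no replacement, or with six patients at the other dose level and the ceiling of 26 respected, alpha stays at 0.087.

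Arm 1 has no success rule, so no alpha is at stake there. Severity is minor to should-fix.

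**What to change.** 1. **Section 5.9, arm 2.** Align with 5.4: dosed patients are replaced only for DLT evaluability in the MTD decision, never for ORR. Reconcile the wording on evaluability with 12.1.1.
2. **Section 14.2.** State that the rule of 7 in 20 applies to the first 20 eligible patients dosed at the MTD, counted as in 14.3.2 and including any replaced for DLT evaluability. Change the fixed 14 additional patients to 20 minus the number already dosed at that level. Alpha stays at 0.087 and power at 0.942.
3. **Section 5.9, arm 1.** Replacement need not be deleted. It is enough to say that replaced dosed patients stay in the FAS as non-responders.

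**Alternative to item 2.** If a larger denominator is kept, prespecify 8 responses for N = 21, 22 or 23. Fixed-N alpha is 0.043, 0.056 and 0.072. Power at 50% ORR is 0.905, 0.933 and 0.953, so it falls below the stated 94% at N = 21 and 22.

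**Cost.** A short amendment and no extra patients. Under the preferred fix the reported ORR may be slightly less favourable, and fewer than 20 patients may have a post-baseline scan (about 20 × 0.90 = 18 at an assumed 10% loss).
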